#### **6.5 Limitations of the design, data source, and analysis methods**

Several potential limitations have been identified in the study.

- Selection of a small number of participants. We prioritized a realistic approach for an initial project that is feasible but also sufficiently representative.
- Wide pediatric age range. The influence of the environment outside the family will have some impact on the older population.
- Family diversity. Our goal is to collect data on the real impact and avoid biases based on different family realities. Thus, it is anticipated that data will be collected from patients who live with one or more families.

## 7. DATA MANAGEMENT

### 7.1 Data Collection and Confidentiality

Data will be entered by the researchers themselves and/or authorized personnel directly into the EDC. To ensure the confidentiality of the data obtained from the study, only the local researcher and their team of collaborators, the sponsor or their designated person, the REC, the relevant health authorities, and those responsible for data analysis will have access to them.

Regarding the EDC, each researcher will be provided with a username and a password consisting of between 4 and 6 digits in a sealed document. These codes are considered confidential and non-transferable and are subject to the same confidentiality rules as all other documents, including the protocol. Researchers are responsible for keeping their passwords confidential and not disclosing them to third parties. To gain access to the EDC, researchers must sign the study investigator commitment and confidentiality agreement.

The content of the EDC, as well as the documents generated during the study and the database, will be protected from unauthorized use by persons outside the research project and, therefore, will be considered strictly confidential and will not be disclosed to third parties. Furthermore, the EDC will be automatically disconnected if there is no activity for more than 10 minutes. This will protect the EDC from unauthorized access, should the study investigator leave the EDC open for any reason.

Patients included at each center will have a consecutive number (code), automatically generated by the EDC once the informed consent form has been signed and the EDC inclusion criteria have been met. This patient code will be documented in the participant's medical record and in the confidential patient inclusion record in the investigator's folder at each participating center.

### 7.2 Mandatory requirements of the Data Protection Act, Regulation (EU) No. 2016/679, and Organic Law 3/2018 on the Protection of Personal Data and Guarantee of Digital Rights (GDPR)

#### 7.2.1 *Identification of the data and the subjects who process them*

The variables required to carry out the study are those specified in the variable section (Table 1) and will be collected from the participants after obtaining informed consent and collecting data through the EDC during follow-up visits. The information will be coded. Coding will be done through the EDC as specified in section 7.1 Data collection and confidentiality.

#### 7.2.2 *Identification of the processing and legitimate basis for processing*

The processing of the personal data required in this study is governed by Organic Law 3/2018, of December 5, on the protection of personal data. The principal investigator of the study and the sponsor, the Institut de Recerca Sant Pau (IR SANT PAU), [name], [contact], act as data controllers within the framework of this study. The data ultimately recorded in the central database will remain the property of the sponsor. The identity of the participants will not be revealed to any other person except to the health authorities, when required or in cases of medical emergency. The Research Ethics Committees, representatives of the Health Authority for inspection purposes, and personnel authorized by the sponsor will only have access to the data to verify personal data, clinical study procedures, and compliance with good clinical practice standards (always maintaining the confidentiality of the information).

The researcher and the sponsor are required to retain the data collected for the study for at least 5 years after its completion. Subsequently, personal information will only be retained by the patient's healthcare center and the sponsor for other scientific research purposes if the patient has given their consent to do so, and if permitted by applicable law and ethical requirements.

Legal basis for processing: GDPR: 6.1 a) the data subject has given their consent to the processing of their personal data for one or more specific purposes.

#### *7.2.3 Tools used to process data*

The REDCAP platform will be used to carry out the project. It is hosted on the servers of the sponsor, the IR Sant Pau, and is implemented with the security measures established by the institution. The data is stored on the local web server where the organization has installed the software and is therefore only accessible on computers with a trusted connection via VPN and secure credentials (certificates, RSA keys, or complex passwords).

#### *7.2.4 International data transfers*

There will be no international data transfers.

#### *7.2.5 Identification of processing operations that may pose a high risk to the rights and freedoms of participants in the research project*

In accordance with Article 35 of the GDPR, the project does not meet the requirements that require the corresponding impact assessment.

#### *7.2.6 Rights of data subjects*

In accordance with Regulation (EU) No. 2016/679 and Organic Law 3/2018 on the Protection of Personal Data and the Guarantee of Digital Rights, patients may limit the processing of inaccurate data, request a copy, or request the transfer of the data they have provided for the study to a third party (portability). To exercise these rights, you must contact the principal investigator, the researchers at the study site, or the center's Data Protection Officer, where applicable, at the center or sponsor: IR SANT PAU, [name], [contact], email: [dpo\\[contact]](mailto:[contact]), or the Spanish Data Protection Agency at [name] (<https://www.aepd.es/es>) or the Catalan Data Protection Authority (<https://apdcat.gencat.cat>).

If the participant wants to know more about it, he/she can contact the Data Protection Officer of the institution or the promoter IR SANT PAU, [name], [contact], email: [[contact]](mailto:[contact]), or with the Spanish Data Protection Agency at [name] (<https://www.aepd.es/es>) or the Catalan Data Protection Authority (<https://apdcat.gencat.cat>).

#### *7.2.7 Data Validation and Quality Control*

All data received through the use of the EDC will be stored and subject to the appropriate working procedures to comply with FDA standard 21 CFR Part 11, thereby guaranteeing their confidentiality, security, and authenticity. The adaptation of the 21 CFR Part 11 standard ensures that data received via electronic transmission is as valid as original data received on paper. This standard establishes the rules for the use of electronic data and defines the requirements for all systems for their collection, storage, maintenance, and security.

All data entered by the researcher in the system will be reviewed by an automatic validation program, and discrepancy reports will be generated accordingly to facilitate correct and complete data entry (automatic queries). Furthermore, the entered data will be reviewed and verified by the study monitor. Corrections to the EDC will be made by the researchers themselves. The original data must be available and ready for review during scheduled monitoring visits.

Furthermore, all documents related to this study must be made available to the appropriately qualified personnel responsible for conducting any audits or inspections that may be carried out. Verification of the ECR data must be performed by direct inspection of the original documents.

## **8. WORK PLAN (tasks, milestones, and study timeline)**

This project is divided into phases:

*Phase 1 (April 2024 - April 2026): Recruitment.*

Recruitment will begin in February, the expected date for obtaining the IRB documentation from each center. This period will last two years.

*Phase 2 (April 2024 - April 2026): First visit.*

Once the participants have been recruited and have signed the IRB, their first visit will include completing the questionnaires, interview, and physical examination. This first visit will take place no more than one week after the child's T1D diagnosis.

*Phase 3 (September 2024 - September 2026): Follow-up.*

The follow-up visit will take place 6 months after the first visit. The questionnaires, interview, and physical examination will be repeated.

*Phase 4 (April 2025 - April 2027): Final visit.*

The final visit will be conducted 12 months after the first visit. The questionnaires, interview, and physical examination will be repeated.

*Phase 5 (September 2026 - April 2027): Data analysis.*

In the final part of the study, the data of the patients who completed the final visit will be analyzed. This will begin with database cleaning and management, analysis, and subsequent interpretation and discussion of the results.

*Phase 6 (April 2027): Study closure.*

Once all final visits are completed, data analysis will be finalized, and communications and manuscripts will be prepared. A research meeting will be held to prepare the final report and close the study.

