### 4.3 Secondary objectives:

\*Due to the timeliness of the study, we also proposed:

- To characterize changes in the dietary patterns of parents or guardians of patients with T1D during follow-up (6 months after diagnosis).
- To determine, using a questionnaire, changes in the physical activity of the adult subjects in the study at 6 and 12 months.
- To determine, using a questionnaire, the emotional stress produced by the diagnosis and treatment of T1D in the adult parents or guardians belonging to the families of the incident case at 6 and 12 months.
- To determine, using a questionnaire, the level of anxiety and depression produced by the diagnosis and treatment of T1D in the adults in the families at 6 and 12 months.

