### 6.3 Data Analysis

Data validation and quality control will first be performed through a descriptive analysis, expressing frequencies and extreme values for all recorded variables. Any errors detected will be corrected through a search for and recovery of missing data and an analysis of inconsistencies. Subsequently, a description of the sample will be provided, expressing the frequency distribution of the qualitative variables, and the arithmetic mean, median, and standard deviation, as well as maximum and minimum values for the quantitative variables.

The main analysis will consist of estimating the frequency and/or mean of post-treatment changes (reduction/increase). A paired data analysis of the changes will also be performed. A mixed-effects analysis (linear link GLM) will be performed for continuous variables. This same analysis will be performed for other dichotomous efficacy variables (improvement or lack thereof in each parameter) using logistic link GLM models. In addition, for the comparative analysis from time 0 to 6 months, parametric and nonparametric comparison tests (Student's t-test, chi-square, Wilcoxon test) and linear regressions will be applied to observe the influence between variables, taking into account the follow-up time. Family units will be phenotyped based on their variables by creating clusters using the k-means algorithm.

In all analyses, a type I error or  $\alpha$  of 5% will be established, with statistical significance when p values are less than 0.05, and a type  $\beta$  error of 20% (statistical power of 80%). Statistical analyses will be performed using the R Core Team statistical package (2023) v. 4.3.

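### Read literally, Phase 5 of the work plan analyses only those who complete month 12, which drops usable 6-month data; the protocol should say whether this is scheduling or an analysis set

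*Protocol*

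**What the plan says.** Protocol Section 8 describes Phase 5, the data-analysis phase, with the words "the data of the patients who completed the final visit will be analyzed". Under Phase 4 of the same section, "The final visit will be conducted 12 months after the first visit". This is the only place in the protocol that says whose data enter the analysis.

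Three other parts bear on it:

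- **Objectives (4.3).** The first secondary objective is "To characterize changes in the dietary patterns of parents or guardians of patients with T1D during follow-up (6 months after diagnosis"). The second concerns "changes in the physical activity of the adult subjects in the study at 6 and 12 months". The stress objective and the anxiety and depression objective carry the same two time points. Table 2 in Section 6.2 schedules every questionnaire at baseline, 6 months and 12 months.
- **Analysis (6.3).** "A mixed-effects analysis (linear link GLM) will be performed for continuous variables", and "for the comparative analysis from time 0 to 6 months, parametric and nonparametric comparison tests" are planned. Neither is tied to attendance at month 12. The only words on missing data concern cleaning: a "search for and recovery of missing data and an analysis of inconsistencies".
- **Withdrawal (5.5.3).** A participant may withdraw and may, in addition, revoke the use of the data already given.

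**The concern.** A parent seen at baseline and at 6 months, but not at 12, has everything that the 6-month objectives require. Under the literal reading of Phase 5 that parent is absent from the 6-month diet, activity, stress and anxiety results, and the parent's two observed visits do not reach the mixed model. A 6-month result would then depend on attendance six months later, and the protocol gives no reason for that condition.

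Selective attendance is plausible here. The Background (Section 3) reports, for families of very young patients, that stress goes with lower adherence to dietary recommendations, and both stress and diet are outcomes of this study. If families who struggle are less likely to return at month 12, the results would describe the retained families rather than the enrolled ones. The recruitment target also equals the calculated sample size of 26 units, with no stated allowance for loss, so each discarded pair counts.

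**Working it through.** **Step 1. Who is kept under each part of the protocol.** The table sets the literal reading of Phase 5 beside what Sections 4.3 and 6.3 could use.

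| Visits attended | Phase 5, literal | 0-to-6-month comparison (6.3) | Mixed model (6.3) |
|---|---|---|---|
| 0, 6, 12 | in | usable pair | three visits |
| 0, 12 | in | no pair | two visits |
| 0, 6 | **out** | **usable pair** | **two visits** |
| 0 only | out | no pair | one visit |

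The third row is the conflict: a complete 6-month pair that a 6-month objective needs and that Phase 5 leaves out. The fourth row matters less, but a mixed model can still use the baseline value. Section 5.5.3 points the same way. Revoking data use would add little as a separate step if leaving before month 12 already removed the data. Data recovery during cleaning (6.3) cannot recover a visit that never took place.

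**Step 2. The plan's own figure.** Section 6.4 gives 26 units to detect 1 aMED point with a paired test at 80% power and 5% alpha. It prints no standard deviation (SD), so the 26 cannot be reproduced. Solved backwards with a two-sided paired t-test, it corresponds to an SD of change of about 1.71 to 1.75. The present point does not depend on that value.

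**Step 3. What the literal rule itself costs.** Inputs: 26 units (6.4); an assumed share p missing month 12 (the protocol gives none); and the assumption that all of them attended month 6. Pairs lost = 26 × p. With the SD of change held fixed, the standard error of the mean 6-month change grows by √(26 / pairs kept).

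| p (assumed) | Pairs lost | Pairs kept | Standard error ratio |
|---|---|---|---|
| 10% | 2.6, about 3 | 23 | √(26/23) = 1.06 |
| 20% | 5.2, about 5 | 21 | √(26/21) = 1.11 |
| 30% | 7.8, about 8 | 18 | √(26/18) = 1.20 |

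If some of these families had also missed month 6, the loss of pairs would be smaller.

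**Step 4. What cannot be charged to the rule.** For the 12-month change, let completers change by 1.0 aMED point and non-completers by c. The mean over all enrolled is (1 − p) × 1.0 + p × c, while a completers-only analysis reports 1.0. All inputs are assumed.

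| p | c = 0 | c = 0.5 | c = 1.5 |
|---|---|---|---|
| 10% | 0.90 | 0.95 | 1.05 |
| 20% | 0.80 | 0.90 | 1.10 |
| 30% | 0.70 | 0.85 | 1.15 |

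The sign of the gap follows from the choice of c, which the document does not supply. The 12-month values of non-completers are also unobserved whichever analysis set is chosen. A mixed model that includes their earlier visits narrows the gap only to the extent that those visits explain who drops out.

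**The case against.** The strongest reply is that Phase 5 is scheduling. Section 8 is a work plan with milestones. Phase 5 (September 2026 to April 2027) overlaps Phase 4 (April 2025 to April 2027), so some families will still be in follow-up when analysis begins, and it is natural to say that work proceeds on those who have finished. Phase 6 has the analysis finalised once all final visits are done. The sentence does not say that only completers count, and Section 6.3 plans its 6-month comparison and mixed model without any such condition. This stands: a reader might infer that the protocol has firmly adopted a completers-only analysis, and the document does not support that degree of certainty.

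The reply does not settle the matter. Someone who never attends month 12 never becomes a person who completed the final visit, and nothing else in the protocol brings that person back in.

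A second reply is that analysis sets and rules for missed visits are commonly left to a statistical analysis plan, which is not shown. That is right as far as omissions go. The point rests instead on a sentence the protocol does contain, which pulls against 4.3, 6.3 and 5.5.3.

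A third is that visits are placed as close as possible to routine check-ups (5.3), which should limit attrition. It may, but the protocol states no expected rate.

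**Conclusion.** The point holds as an ambiguity with a definite cost under its literal reading. That cost is the 6-month pairs and partial series of anyone who misses month 12. At an assumed 20% loss with full attendance at month 6, this is about 5 of 26 pairs, with a standard error about 11% larger for the 6-month change. Over assumed losses of 10% to 30%, about 3 to 8 pairs go.

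A reader might go further and infer that the rule makes the 12-month aMED change look larger than it is by some stated percentage. The documents do not support that. They give neither a dropout rate nor any value for non-completers, so both the direction and the size of the bias are unknown. Most of any such gap would come from values that no analysis set can recover.

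The sponsor should still correct the sentence. Leaving both readings open allows the analysed group to be chosen after the data are seen, and the correction uses data and a model already planned.

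**What to change.** Replace the Phase 5 sentence in Section 8 (or place the rule in 6.3 and refer to it) with:

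> Data from all enrolled participants are analysed, except data whose use has been revoked (5.5.3). The mixed model of 6.3 uses every observed visit, including those of participants who miss month 6 or month 12. The 0-to-6-month analyses include everyone with baseline and 6-month data, whether or not they attend month 12. An analysis of month-12 completers is a sensitivity analysis.

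If the sentence was meant only as timing, reword it to say that analysis work begins as participants complete their final visit.

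The cost is a short text change through a written amendment (Section 12), with no added visits, data or models. It restores all observed 6-month pairs. For the 12-month change it reduces bias only as far as the observed visits explain the dropout, and it should not be presented as removing it.

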## **9. ETHICAL ASPECTS:**

This study complies with all ethical aspects and the protection of participating subjects by complying with the ethical precepts formulated in Royal Decree 957/2020 and the Biomedical Research Law 14/2007, of July 3, and in the Declaration of Helsinki and all its revisions.

Given that this study is observational in nature, patient participation is considered to entail minimal risk, i.e., the risk is similar to that which the patient would have in clinical practice without participation in the study. It is an unconditional prerequisite for a patient's participation to obtain their consent after having been informed

by the researcher about the information, both verbally and in writing, in a language that allows its content to be fully legible and understandable to the patient.

The protocol will be submitted for evaluation by a Research Ethics Committee prior to the start of patient enrollment. Any data required by the protocol may be subject to audits by the sponsor, independent organizations, and/or competent authorities, but data confidentiality, in accordance with the aforementioned law, will always be an essential condition.

Participating subjects may revoke their consent for the use of their data in the analysis at any time, without giving reasons and without incurring any liability or harm.

Before accepting and signing the researcher's commitment, participating clinicians must ensure that their participation in the study does not interfere with their prescribing habits or their healthcare duties.

### **9.1 Benefit-Risk Assessment of the Research**

This project addresses the priority of developing personalized medicine. This project adopts a research approach that is clearly aimed at improving clinical decision-making that affects the people we serve. The potential impact may be equivalent to that mentioned for diabetes itself. The patient will not be at risk in this study as it is entirely observational and therefore will not be subject to any intervention, whether dietary or pharmacological. This study is limited to recording anonymized data in a database that does not allow access to the patient's personal data.

### **9.2 Ethical Considerations, Regarding Subject Information and Informed Consent**

The study will be conducted in strict accordance with international ethical recommendations for medical research involving humans. The researcher will be responsible for ensuring that the study is conducted in accordance with the standards set forth in the Declaration of Helsinki.

Before starting the study, the Research Ethics Committee of the HSCSP must approve the study protocol, the information that will be provided to the subject, and the informed consent form that will be used.

The Research Ethics Committee will be informed of any subsequent amendments to the protocol and should be requested if a further evaluation of the ethical aspects of the study is necessary.

It is the researcher's responsibility to obtain the patient's informed consent. The patient may not participate in any specific study procedure without obtaining their consent or that of their legal guardian/family member if the patient is unable to give consent due to their clinical condition.

Before including any subject in the study and before obtaining informed consent, the researcher or a person designated by the researcher will explain the objectives, methods, potential risks of the study, and any discomfort it may cause to the potential participant or their legal guardian/family member. The nature, scope, and potential consequences of the study will be explained in understandable language. Rights related to data protection law will be explained, as will the possibility of being contacted in the case of future studies related to diabetes. The potential participant or their legal guardian/family member must be given time to consider their decision to participate in the study and have the opportunity to ask questions. After this explanation, and before entering the study, consent must be properly recorded by the signature of the subject or their legal guardian/family member. The informed consent must be signed in three copies: one for the participant, one for the researcher, and the third copy for the biobank.

